At the first visit (Day 1), subjects will complete the informed consent. A pregnancy test will be administered to women of childbearing potential, and the site physician or study site personnel will confirm subject eligibility criteria. Following this, the site physician or study site personnel trained in the use of *REDCap Cloud* will assist each subject in creating a *REDCap Cloud* account and completing the baseline assessment (Appendix 1). The first visit (Day 1) will assess important baseline information, including demographics, chronic pain classification, cannabis experience, concomitant medications, treatment goal, and ST treatment regimen. Subjects will complete the Brief Pain Inventory-Short Form (BPI-SF) and Euro- Quality of life Assessment (EQ5DL) at this visit.

At each subsequent physician-verified visit (a total of 4), the site physician or study site personnel will assist with the completion of physician follow-up assessment (Appendix 2) via *REDCap Cloud*, and reassess ST treatment regimen, concomitant medications, effectiveness and tolerability of the ST treatment regimen (including AEs & SAEs). Subjects will complete the BPI-SF, EQ5DL, and Patient Global Impression of Change (PGI-C) and physicians will complete the Clinical Global Impression-Improvement (CGI-I).

Four subject-verified follow-up assessments will be completed by subjects via the *REDCap Cloud* online portal (Appendix 3). Subjects will receive an automated email one week prior and the day of subject-verified follow-up with a reminder to complete the online assessment. The subject-verified online assessment will include questions about their ST treatment regimen, additional cannabis consumption, numeric rating scale (NRS) pain items of the BPI-SF, the EQ5D-5L, and the PGI-C.

Spontaneous AE reporting will be entered in *REDCap Cloud* by the subject during subject follow-up assessments, using the Subject AE log (Appendix 3). Physicians will verify and assess all AEs entered at physician follow-ups, using the Physician AE form (Appendix 2). All serious adverse events will be sent directly to Canopy Growth's Global Pharmacovigilance Department (GPVD) in real-time, where they will be reviewed with respect to country specific regulatory requirements. All non-serious adverse events will be sent in a monthly report to GPVD.

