7. OUTCOME ASSESSMENTS

7.1 Study Endpoints

Primary endpoints

- Physician selection of Spectrum Therapeutics (ST) medical cannabis treatment regimen and changes over time in:
 - (1) average daily dose of THC and CBD (in mg);
 - (2) route of administration (inhaled or ingested).

Secondary endpoints

- Subject selection of ST treatment regimen and changes over time in:
 - (1) average daily dose of THC and CBD (in mg);
 - (2) route of administration (inhaled or ingested).
- Change in BPI-SF responses from baseline.
- Change in EQ5D-5L responses from baseline.
- PGI-C for the target treatment goal.
- CGI-I for the target treatment goal.
- In subjects taking an opioid, changes in opioid use over time (calculated as milligram morphine equivalents [MME]/day).
- Among subjects taking other medication, total daily dose change over time.

Safety endpoint

- Incidence of AEs stratified by product and formulation.

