7.2.5 Determination of Opioid Consumption

Physicians will confirm subjects who take an opioid at baseline or who start an opioid during the study, and will be asked to report the opioid type and MME, so that opioid consumption (and any opioid-sparing effect of the ST treatment regimen) can be examined over time.

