What is their current daily dose of [baseline_visit]
[musrel1_name] (total mg per day)?

At last visit, you indicated that your patient was taking
[baseline_visit][musrel2_name]. Is your patient still taking this
medication?

- Yes
- No

Please select the reason why your patient stopped taking this
medication.

- Side effects
- Cost
- Lack of benefit
- No longer needs/ replaced by medical
cannabis
- Unknown

What is their current daily dose of [baseline_visit]
[musrel2_name] (total mg per day)?

At last visit, you indicated that your patient was taking
[baseline_visit][musrel3_name]. Is your patient still taking this
medication?

- Yes
- No

Please select the reason why your patient stopped taking this
medication.

- Side effects
- Cost
- Lack of benefit
- No longer needs/ replaced by medical
cannabis
- Unknown

What is their current daily dose of [baseline_visit]
[musrel3_name] (total mg per day)?

Existing Benzodiazepines Dosing Information

At last visit, you indicated that your patient was taking
[baseline_visit][benzo1_name]. Is your patient still taking this
medication?

- Yes
- No

Please select the reason why your patient stopped taking this medication.

- Side effects
- Cost
- Lack of benefit
- No longer needs/ replaced by medical cannabis
- Unknown

What is their current daily dose of [baseline_visit] [benzo1_name] (total mg per day)?

At last visit, you indicated that your patient was taking [baseline_visit][benzo2_name]. Is your patient still taking this medication?

- Yes
- No

Please select the reason why your patient stopped taking this medication.

- Side effects
- Cost
- Lack of benefit
- No longer needs/ replaced by medical cannabis
- Unknown

What is their current daily dose of [baseline_visit] [benzo2_name] (total mg per day)?

At last visit, you indicated that your patient was taking [baseline_visit][benzo3_name]. Is your patient still taking this medication?

- Yes
- No

Please select the reason why your patient stopped taking this medication.

- Side effects
- Cost
- Lack of benefit
- No longer needs/ replaced by medical cannabis
- Unknown

What is their current daily dose of [baseline_visit] [benzo3_name] (total mg per day)?

Existing Opioid Dosing Information

At last visit, you indicated that your patient had an MME of [baseline_visit][opioid_mme]. Is your patient still taking opioids?

- Yes
- No

Please select the reason why your patient stopped taking this medication.

- Side effects
- Cost
- Lack of benefit

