- No longer needs/ replaced by medical cannabis
- Unknown

What is their current MME?

Existing Other Medications Dosing Information

At last visit, you indicated that your patient was taking other medications, including [baseline_visit][othmed_name]. Is your patient still taking any of these other prescription medications?

- Yes
- No

Please describe any **changes** to their other existing prescription medications since last visit (including changes to total daily dose)

Concomitant Medications - New

Since last visit, has your patient **started** taking any of the following classes of prescription medication (select all that apply)

- Nonsteroidal Anti-inflammatory Drugs (NSAIDs) and Acetaminophen
- Antidepressants (TCA, SNRI, SSRI)
- Anticonvulsants (gabapentin, pregabalin)
- Muscle Relaxants
- Benzodiazepines
- Opioids
- Other
- Medical Cannabis from a Licensed Producer other than Spectrum

Name of new NSAID/Acetaminophen medication (started since last visit)

Daily dose of [physician_1st_follow][nsaid4_name] (total mg per day)

Name of new antidepressant medication (started since last visit)

Daily dose of [physician_1st_follow][antidep4_name] (total mg per day)

Name of new anticonvulsant medication (started since last visit)

Daily dose of [physician_1st_follow][anticon4_name] (total mg per day)

Name of new muscle relaxant medication (started since last visit)

Daily dose of [physician_1st_follow][musrel4_name] (total mg per day)

Name of new benzodiazepine medication (started since last visit)

Daily dose of [physician_1st_follow][benzo4_name] (total mg per day)

Please enter MME (total daily morphine equivalent dose in mg)

Name of new prescription medication (started since last visit, not covered in above classes)

Daily dose of [physician_1st_follow][othmed4_name] (total mg per day)

Physician AE form

Product information

Do you have any adverse events to report related to this patient?

- Yes
- No

Suspect product(s) name

Start date

_____ (YYYY-MM-DD)

End date

_____ (YYYY-MM-DD)

Route of administration

- oral - oil
- oral - softgel
- oral - spray
- oral - beverage
- oral - chocolate
- oral
- inhalation - smoked
- inhalation - vaporized
- inhalation

Dose (please include amount and unit i.e. mg, ml, #softgels, #inhalations, etc.)

Did reaction disappear after reducing the dose or stopping the product ?

- No
- Yes
- Unknown

Did reaction reappear after same product/treatment was restarted?

- No
- Yes
- Unknown

AE description

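### Appendix 2 collects opioid dose in two overlapping MME boxes with no opioid type, so MME/day is ambiguous when a subject adds or changes an opioid

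*Protocol*

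**What the plan says.** Protocol section 7.1 lists as a secondary endpoint: "In subjects taking an opioid, changes in opioid use over time (calculated as milligram morphine equivalents [MME]/day". Section 7.2.5 covers subjects on an opioid at baseline and those who start one during the study. It states that physicians "will be asked to report the opioid type and MME, so that opioid consumption" and any opioid-sparing effect can be examined.

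Section 3.1 assigns the follow-up form: "At each subsequent physician-verified visit (a total of 4", site staff help complete Appendix 2. Table 1 places concomitant medication at Months 2, 4, 8 and 12 and at unscheduled visits.

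The forms hold the following on opioids:

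- **Appendix 1 (baseline):** one total daily MME, with no drug name or type.
- **Appendix 2, existing medication:** a reminder that at the last visit "your patient had an MME of [baseline_visit][opioid_mme", then "Is your patient still taking opioids", then "What is their current MME".
- **Appendix 2, new medication:** if opioids are ticked as started since the last visit, "Please enter MME (total daily morphine equivalent dose in mg".

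The five other named drug classes in the new-medication block are handled differently. Each asks for the drug, for example "Name of new benzodiazepine medication (started since last visit", and then for that drug's dose.

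**The concern.** Two boxes on one form both appear to ask for the patient's whole opioid dose, and nothing in the protocol says how they relate. This does no harm in a subject whose opioid stays the same. It matters in subjects who add or switch an opioid, and these are subjects whose MME/day trajectory the endpoint is meant to describe. Without an opioid name or type, the data themselves do not show what the second entry covers.

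The prompt raises a separate issue. It draws the last-visit dose from the baseline record, so from the second physician contact onward the printed form may show the physician a reference value that is out of date. At stake is the accuracy of a secondary endpoint from which the protocol intends to judge opioid sparing.

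**Working it through.** The protocol gives no MME values, so there is no stated figure to reproduce. The check compares the fields and then uses assumed doses to show how far the readings diverge.

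**Fields compared**

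Call the existing-medication entry box A and the new-medication entry box B.

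- Box A follows a question about any opioid, not about the opioid recorded at baseline. Read literally, it is the patient's current total. A physician who takes the block's heading as the guide could enter only the opioid already in use.
- Box B carries the same wording as the baseline total. Read literally, it too is the patient's total. A physician who follows the pattern of the other classes in that block would enter only the new opioid.

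**Addition (assumed doses)**

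Day 1 dose 60 MME, 20 MME added later. True total 60 + 20 = 80; true change 80 − 60 = +20.

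| Box A read as | Box B read as | A | B | A + B | A alone | B alone |
|---|---|---|---|---|---|---|
| patient total | patient total | 80 | 80 | 160 | 80 | 80 |
| patient total | new opioid only | 80 | 20 | 100 | 80 | 20 |
| old opioid only | patient total | 60 | 80 | 140 | 60 | 80 |
| old opioid only | new opioid only | 60 | 20 | 80 | 60 | 20 |

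Derived values run from 20 to 160. Derived change runs from 20 − 60 = −40 to 160 − 60 = +100, against a true +20. No single rule (add, A only, B only) gives 80 in all four rows.

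**Rotation (assumed doses)**

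60 MME of one opioid is replaced by 60 MME of another. True total 60; true change 0. The subject is still taking opioids, so A = 60. If the physician also records an opioid as started, B = 60. Adding gives 60 + 60 = 120, a false change of 120 − 60 = +60. Taking either box alone gives the correct 60.

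**Prompt by visit, as printed**

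- Month 2: Day 1 is normally the last physician visit, so the prompt is right unless an unscheduled visit came between.
- Months 4, 8 and 12: the last visit was Month 2, 4 or 8, but the prompt still refers to the baseline record. A subject who stopped by Month 2 would again be shown the Day 1 dose.
- Opioid started after Day 1: box B can take it once. At the next visit it is no longer new since the last visit, and the existing-medication prompt refers only to the baseline MME, so no printed prompt refers to it.

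**Opioid type**

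Section 7.2.5 says it is reported. Neither Appendix 1 nor Appendix 2 has a field for it.

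**The case against.** - **The boxes may not overlap in use.** The new-medication question asks about classes of drug started. On one reading, a baseline opioid user who rotates has not started the class, so box A holds the total and box B serves only subjects new to opioids. REDCap Cloud uses skip logic (section 8.2), and a flat printout cannot show which fields appear together. This is a fair reading, but the form does not settle on it: the other classes in the same block ask about an individual new drug.
- **Nothing says the boxes are added.** Correct. A reader might infer that the endpoint will be double-counted. The documents do not support that, since no passage describes summing and the combining rule may sit in the SAP, which is not shown. What stands is that a later rule can choose a box or a sum, but cannot tell from the entries what box B meant.
- **The printed form may be the first follow-up only.** Some field names in Appendix 2 refer to the first physician follow-up, so later screens may be filled differently. This limits the prompt issue but not the two-box issue, which is present at the first follow-up too. Section 3.1 names Appendix 2 for all four visits and the protocol prints no other version.
- **Queries and monitoring exist.** Section 8.2 provides for queries on missing, implausible or inconsistent data and section 8.3 for continuous remote monitoring, so it would go too far to say that errors could never be corrected. However, pairs such as 60 and 60, or 80 and 20, are individually plausible, and source verification covers only 10% of sites.
- **The outdated prompt may be harmless.** A reader might infer that it pulls later entries towards baseline. Nothing in the documents shows this; the physician is still asked for the current dose. Nor does the prompt cause double-counting. The two faults are separate.

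**Conclusion.** The point holds as an ambiguity in data capture for a named secondary endpoint, in three parts.

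1. The two MME boxes have no stated relation. For a subject who adds or rotates an opioid, the derived MME/day can be too high or too low. With the assumed 60 plus 20 MME, it can fall anywhere from 20 to 160 against a true 80. These are single-patient illustrations. The documents do not say how often opioids are added or switched, so the effect on the endpoint as a whole cannot be sized.
2. The printed prompt presents the Day 1 dose as the last-visit dose. This is normally right at Month 2 and outdated at Months 4, 8 and 12, provided that the later screens match the printed form. It also makes no reference to an opioid started after Day 1.
3. Section 7.2.5 and the forms contradict each other on opioid type.

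The change is worth making because it is cheap and because an analysis rule alone cannot fully resolve the first part.

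**What to change.** At every physician visit, and for every subject, use one mandatory field: *Total MME/day from all opioids (0 if none)*. Prompt it with the value from the most recent completed physician visit, including unscheduled ones. Remove the MME box from the new-medication block and keep there only a yes/no for an opioid started or changed since the last visit. Add the opioid type field that section 7.2.5 already promises to Appendices 1 and 2. If later follow-up screens already draw on the preceding visit, say so in the appendix.

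The cost is a small eCRF revision. The physician completes one dose box instead of two, plus the type entry that the protocol already expects. If visits have already been recorded on the present form, those with both boxes filled would need a site query to establish what the second entry covered.

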Appendix 3 – SUBJECT-VERIFIED FOLLOW-UP ASSESSMENT

ST Regimen Canada

[figure not shown]

[figure not shown]
[figure not shown]

[figure not shown]

Please enter in the table below total daily amount of Spectrum Therapeutics products consumed. Please be conscious of the units provided:

Inhaled cannabis = total number of inhalations per day

Ingested oils = total mL per day

Spray format = total number of sprays per day

Capsules & edibles = total number of capsules or total number of chocolate bar squares per day

Physician-recommended Regimen of Spectrum Therapeutics Products					
	Inhaled Formats (dried flower, extract vaporizers) -- report daily total number of inhalations	Ingested Oil Formats - report daily total number of mLs	Spray Formats - report daily total number of sprays	Low Potency Capsule & Edible Formats - report daily total number of low-potency capsules (i.e. 2.5 mg), number of chocolate bar squares, etc.	High Potency Capsule Formats - report daily total number of high-potency capsules
Red (examples include Spectrum #1-4; Tweed Bakerstreet, Highlands, Houdstooth, Donegal; LBS Sunset)	 inhalations  	 mL  	 sprays  	 capsules  	 capsules  
Orange	 inhalations  		 sprays  		
Purple (examples include LBS Ocean View)	 inhalations  		 sprays  		
Blue (examples include Tweed Penelope)	 inhalations  	 mL  	 sprays  	 capsules  	 capsules  
Green (examples include Tweed Argyle)	 inhalations  	 mL  	 sprays  	 capsules  	 capsules  
Yellow (examples include Tweed CBD Softgels)	 inhalations  	 mL  	 sprays  	 capsules  	 capsules  
Spectrum Clear (or White)		 mL  			

You indicated that your patient has been recommended an inhaled format. Please identify their most common method of administration.
(inhal_admin)
[Branching logic exists]

Smoked
 Dried flower vaporizer (e.g. Stroz and Bickel, PAX)
 Extract vaporizer (e.g. vape pen cartridge)

Do you or your patient know the temperature set point of the vaporizer (in °C)

Yes
 No

(inhal_vape_Y/N)
[Branching logic exists]

If known, please provide the temperature set point of your patient's vaporizer (in °C) _____

(inhal_vape_temp)
(125 / 300)
[Branching logic exists]

Calculated, approximated total daily dose of THC and CBD (in mgs)		
	THC	CBD
Inhaled	(inhal_THC)  View Equation	(inhal_CBD)  View Equation
Ingested	(ingest_THC)  View Equation	(ingest_CBD)  View Equation

Side Effects

Does your daily dose include any side effects (e.g. nausea, dry mouth, drowsiness, euphoria, etc.)?

- Yes
- No

You indicated that you experience side effects from your daily dose. Please indicate which side effects you experience (check all that apply)

- Nausea
- Dry Mouth
- Dizziness
- Somnolence (i.e. sleepiness/drowsiness)
- Euphoria
- Other

Please describe the 'other' side effects that you experienced

Subject Adverse Event Reporting

AE diary

Since you have been taking Spectrum Therapeutics medical cannabis products, have you experienced any side effects? Please include any side effects you have experienced, regardless of whether you believe they are related to medical cannabis.

- Yes
- No

Please describe in as much detail the adverse event (side effect) that you experienced.

Adverse events, symptoms, start date/end date, event(s) chronology, treatments, outcome.

PGI-C

Global Impression of Change

Since the start of Spectrum Therapeutics treatment, my overall symptom status is:

(best describe how your symptom is now, compared with how it was before you began taking medical cannabis)

- Very Much Improved
- Much Improved
- Minimally Improved
- No Change
- Minimally Worse
- Much Worse
- Very Much Worse

Patient reported outcomes

BPI

Throughout our lives, most of us have had pain from time to time (such as minor headaches, sprains, and toothaches). Have you had pain other than these everyday kinds of pain today?

- Yes
- No

Please select the number (0= no pain, 10= pain as bad as you can imagine) that best describes your pain at its worst in the last 24 hours.

- 0
- 1
- 2
- 3
- 4
- 5
- 6
- 7
- 8
- 9
- 10

Please select the number (0= no pain, 10= pain as bad as you can imagine) that best describes your pain at its least in the last 24 hours.

- 0
- 1
- 2
- 3
- 4
- 5
- 6
- 7
- 8
- 9
- 10

Please select the number (0= no pain, 10= pain as bad as you can imagine) that best describes your pain on the average.

- 0
- 1
- 2
- 3
- 4
- 5
- 6
- 7
- 8
- 9
- 10

Please select the number (0= no pain, 10= pain as bad as you can imagine) that best describes how much pain you have right now.

- 0
- 1
- 2
- 3
- 4
- 5
- 6
- 7
- 8
- 9

Please select the number (0= does not interfere, 10= completely interferes) that best describes how, during the past 24 hours, pain has interfered with your: **General Activity**

- 0
- 1
- 2
- 3
- 4
- 5
- 6
- 7
- 8
- 9
- 10

Please select the number (0= does not interfere, 10= completely interferes) that best describes how, during the past 24 hours, pain has interfered with your: **Mood**

- 0
- 1
- 2
- 3
- 4
- 5
- 6
- 7
- 8
- 9
- 10

Please select the number (0= does not interfere, 10= completely interferes) that best describes how, during the past 24 hours, pain has interfered with your: **Walking ability**

- 0
- 1
- 2
- 3
- 4
- 5
- 6
- 7
- 8
- 9
- 10

Please select the number (0= does not interfere, 10= completely interferes) that best describes how, during the past 24 hours, pain has interfered with your: **Normal work (includes both work outside the home and housework)**

- 0
- 1
- 2
- 3
- 4
- 5
- 6
- 7
- 8
- 9
- 10

Please select the number (0= does not interfere, 10= completely interferes) that best describes how during the past 24 hours, pain has interfered with your: **Relations with other people**

- 0
- 1
- 2
- 3
- 4
- 5
- 6
- 7
- 8
- 9
- 10

Please select the number (0= does not interfere, 10= completely interferes) that best describes how during the past 24 hours, pain has interfered with your: **Sleep**

- 0
- 1
- 2
- 3
- 4
- 5
- 6
- 7
- 8
- 9
- 10

Please select the number (0= does not interfere, 10= completely interferes) that best describes how during the past 24 hours, pain has interfered with your: **Enjoyment of life**

- 0
- 1
- 2
- 3
- 4
- 5
- 6
- 7
- 8
- 9
- 10

EQ5D

Mobility

- I have no problems in walking about
- I have slight problems in walking about
- I have moderate problems in walking about
- I have severe problems in walking about
- I am unable to walk

Self-Care

- I have no problems washing or dressing myself
- I have slight problems washing or dressing myself
- I have moderate problems washing or dressing myself
- I have severe problems washing or dressing myself
- I am unable to wash or dress myself

Usual Activities

- I have no problems doing my usual activities
- I have slight problems doing my usual activities
- I have moderate problems doing my usual activities
- I have severe problems doing my usual activities
- I am unable to do my usual activities

Pain/Discomfort

- I have no pain or discomfort
- I have slight pain or discomfort
- I have moderate pain or discomfort
- I have severe pain or discomfort
- I have extreme pain or discomfort

Anxiety/Depression

- I am not anxious or depressed
- I am slightly anxious or depressed
- I am moderately anxious or depressed
- I am severely anxious or depressed
- I am extremely anxious or depressed

We would like to know how good or bad your health is TODAY. Please write a number between 0 and 100.

100 means the best health you can imagine

0 means the worst health you can imagine

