3. STUDY DESIGN

3.1 Description of the Study

The present study is a prospective, observational registry designed to generate real-world data on the physician-recommended use of ST products to manage chronic pain in countries where these products are commercially available. The study will enroll up to 1500 subjects from 50-150 sites in geographic regions of ST product distribution over a two-year period. Physicians will recruit subjects during routine care visits and assess whether subjects with chronic pain are candidates for medical cannabis treatment. Once enrolled, subjects will be followed for 1 year to collect data on demographics, chronic pain classification, cannabis experience, treatment goals, concomitant medication(s), ST treatment regimen, clinical assessment, subject-reported outcomes, and safety.

The study includes five physician-verified visits (baseline, 2, 4, 8, and 12 months), and four at-home subject-verified follow-ups (months 1, 3, 6, 10). Physician verified follow ups can be conducted in person or via telemedicine. Additionally, should there be a need, according to the physician's judgement, there may be other unscheduled visits, either in-clinic, or via telemedicine. All data will be collected using *REDCap Cloud* via online eCRFs. The study time-points were selected based on the typical timeframe of titration in routine care, and adverse event (AE) emergence for the use of cannabis products in new subjects; a majority of titration occurs within the first month of taking a new cannabis product²⁹. Visits were also spaced out so that subject retention may be maximized, and treatment adjusted in a timely manner. Later time-points are designed to capture longer-term treatment-related outcomes while screening for AE emergence and medication use changes in the long term.

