9. STATISTICAL METHODS

9.1 Statistical overview

The Sponsor will perform statistical analyses. The Sponsor or designee will extract and analyze descriptive data every 6 months. This will be done to keep sites apprised of study progress. A de-identified summary report will be generated and delivered to all registered site physicians.

The report will indicate:

- The number of physician-collaborators stratified by country.
- The number of subjects enrolled stratified by country.
- Subject demographics, chronic pain classification, and treatment goal.
- Subject concomitant medication use.
- Subject ST treatment regimens.
- Incidence of AEs per individual ST product.

Upon database lock a series of analysis will be conducted to address study objectives. For each analysis, the normality of the data distributions will be ascertained using the Shapiro-Wilk test of normality and Levene's test of equality of error variance. Descriptive statistics (frequencies, means, and standard deviations for normally distributed parametric data; medians and interquartile ranges for nonparametric data) will be used to characterize the sample. Outcome analyses will include a change in ST regimen; a change in reported opioid consumption in MME/day; change in daily dose of other medications, including analgesics, sedatives, and benzodiazepines; change in responses to BPI-SF items and EQ-5DL items; initial PGI-C and changes over time; and initial CGI-I and changes over time. For the safety endpoint, AEs will be tabulated descriptively. Detailed analyses are outlined in the Statistical Analysis Plan.

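### The home adverse event question looks back to the start of treatment every time, so one event can be entered up to four times in the subject log

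*Protocol*

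**What the plan says.** Protocol section 3.1 plans "four at-home subject-verified follow-ups (months 1, 3, 6, 10"), and Table 1 places the subject AE log at each of them. Appendix 3 prints one version of that log. Its question is "Since you have been taking Spectrum Therapeutics medical cannabis products, have you experienced any side effects", and it tells the subject to include events whether or not they are thought to be related. A yes leads to one free-text box with the prompt "Adverse events, symptoms, start date/end date, event(s) chronology, treatments, outcome". The log has no product field and no item separating a new event from one already reported.

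Section 3.1 then requires that "Physicians will verify and assess all AEs entered at physician follow-ups, using the Physician AE form (Appendix 2"). Those visits are at months 2, 4, 8 and 12. The physician form has structured fields for the suspect product, its start and end dates, route and dose, and for the onset and end of the event. Its opening question sets no time limit.

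The safety endpoint in section 7.1 is "Incidence of AEs stratified by product and formulation". The six-monthly site report in section 9.1 includes "Incidence of AEs per individual ST product". On expedited and routine safety flow, section 3.1 says "All non-serious adverse events will be sent in a monthly report to GPVD". Detailed analyses are left to the SAP, which was not available for this review.

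**The concern.** An AE log that is filled in repeatedly should collect each event once. A question whose window never resets does the opposite: a subject who had one short-lived event in the first weeks must answer yes at every later follow-up to be truthful, and is then asked to describe it again. The sponsor's own forms show the alternative. For new medication, Appendix 2 limits the question to the interval, for example "Name of new antidepressant medication (started since last visit").

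What is at stake is the number of events. If a repeat is verified as a separate event, counts of events rise without any new event having occurred. Someone then has to recognise repeats from free text and recalled dates. That is extra work for sites, and an avoidable source of error in a registry that relies on subject entry for AE capture between visits.

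**Working it through.** The protocol states no figure on this point, so there is none to reproduce. The check is a count of recall windows.

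**Inputs**
- Home logs at months 1, 3, 6 and 10 (section 3.1, Table 1).
- Window of each log: start of treatment to the date of the log (Appendix 3).
- Re-entry rate: not given. Let r be the chance that a subject re-enters an event at each later log; r runs from 0 to 1.
- Onset pattern: not given. Constant onset over months 0 to 10 is assumed.
- Every event is assumed to be entered at the first log after onset.

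**Windows that contain an event**

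| Onset | Length (months) | Logs covering it |
|---|---|---|
| Before month 1 | 1 | 4 |
| Months 1–3 | 2 | 3 |
| Months 3–6 | 3 | 2 |
| Months 6–10 | 4 | 1 |

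**Average entries per event with full re-entry (r = 1)**

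(1×4 + 2×3 + 3×2 + 4×1) / 10 = 20 / 10 = 2.0

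**General case.** The first entry counts once and each later log adds r, so the average is 1 + r×(2.0 − 1) = 1 + r. This gives 1.0 at r = 0 and 2.0 at r = 1. The maximum for a single event is 4.

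Section 3.1 places most titration in the first month. If AEs also cluster early, which is an inference and not a statement in the protocol, the full-re-entry average would move above 2.0 towards 4.

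**With a question limited to the interval since the last contact.** Each onset falls in one window, so an event is entered as new at most once.

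**Effect on the tables**
- Counts of events: inflated by whatever share of repeats survives verification.
- Counts of subjects with at least one event under a product: unchanged, because a second record of the same event under the same product adds no subject.
- Attribution to product: unchanged unless a repeat is filed under a different product.

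**Gap between home entry and the next physician visit.** Month 1 to 2 and 3 to 4: 1 month. Month 6 to 8 and 10 to 12: 2 months.

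**The case against.** The best case for the plan is that the subject log is not the final record. Physicians must verify and assess every entry. The subject is prompted for start and end dates and the physician form records onset and end dates, so a repeat can be recognised. This stands, and it is why the figures above describe the raw log and not the endpoint. It does not close the matter: the physician form has no recall window, and the protocol does not ask for entries to be matched to earlier ones.

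A reader might infer that events from an earlier product are carried over to a later one and so distort incidence by product. The protocol does not support that. The subject log names no product; the product is recorded by the physician, with dates. Carry-over would need a physician to re-file an old, dated event under the current product, or the tables to join raw log entries to the current regimen. Canadian subjects may change product freely (section 4.1), so the situation can arise, but the protocol prescribes neither step.

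A reader might also infer that the monthly safety report or the six-monthly site report draws on unverified entries, because verification comes 1 to 2 months later. The protocol does not say which records feed either report.

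Three further points are fair. The SAP may define the counting unit and a rule for duplicates, and their absence from the protocol is not a fault. The printed form might be the month-1 version only, since field names in Appendix 2 refer to the first follow-up; Appendix 3 carries no such label, so this is unproven. Lastly, a cumulative question recovers events that were forgotten earlier. That benefit is real, and the fix should keep it.

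**Conclusion.** The point holds as a minor flaw in form design. As printed, the home AE question invites the same event to be entered up to four times, with an average of 1.0 to 2.0 entries per event under constant onset, depending on an unknown re-entry rate. This rests on the one printed version of Appendix 3 being used at all four home follow-ups.

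The consequence is conditional: AE event counts are inflated only to the extent that repeats are not matched at physician verification. Subject-level incidence within a product is not affected. A biased comparison between products is not shown; it would require one of the two additional errors described above. An SAP rule could limit the damage at analysis, but it cannot change what the form asked, and it would have to work from free text and recalled dates.

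**What to change.** Change Appendix 3 as follows.

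- Month 1: ask about side effects since starting ST.
- Months 3, 6 and 10: *Since your last questionnaire or visit, have you had any new side effects, or any earlier ones you have not yet reported?*
- Add an answer option for an event that is ongoing and already reported.
- Keep the start and end dates.

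In addition, state in the protocol or SAP, if the SAP does not already do so, that physician-verified AE records, matched on onset date, are the source for the incidence tables.

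The cost is one reworded question, one answer option and one sentence on the data source. The question becomes slightly longer. There is a small risk that an event forgotten at one follow-up is missed at the next; the clause on events not yet reported and the physician visits largely cover it.
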